#### **8.4.4 Clinical Laboratory Parameters**

All hematology, coagulation and biochemistry parameters (including PSA and testosterone) will be presented by descriptive statistics in a tabulated summary by time point of assessment for full analysis set together with the respective changes from baseline. In addition, a frequency table for clinically significant values will be presented by time point of assessment.

A by-subject listing for these parameters will be also provided. These listings will be presented for full analysis set and time point and will include: site, subject identifier, laboratory parameter, parameter values (in SI units), SI unit, normal range and a flag with respect to normal range (below, within and above normal range).

#### **8.4.5 Vital Signs**

Weight, systolic and diastolic blood pressure, heart rate and respiratory rate will be presented by descriptive statistics in a tabulated summary by time point of assessment for full analysis set together with the respective changes from baseline. In addition, frequency tables for the number of patients with increases or decreases from baseline in systolic/diastolic blood pressure of  $>20$  mmHg and pulse rate of  $>15$  bpm will be provided by time point of assessment and overall. A by-subject listing for all vital signs for full analysis set and time point will be provided.

#### **8.4.6 Physical Examination**

A frequency table for full analysis set, time point, and body system will be provided for assessment results of normal, abnormal and not done.

A by-subject listing for all body systems for full analysis set and time point will be provided. Only subjects with at least one abnormal finding will be included in this listing.

### **8.5 Handling of missing data**

For time-to-event endpoints, patients without a date of disease progression will be analyzed as censored observations on the date of last tumor assessment. If no post-baseline tumor assessment is available, patients will be censored at the date of first treatment + 1 day. Data for patients with an event (progression) who missed two or more scheduled assessments immediately prior to the event will be censored at the last tumor assessment prior to the missed visits.

For OS, patients who are not reported as having died will be analyzed as censored observations on the date they were last known to be alive. If no post-baseline data are available, OS will be censored at the date of treatment + 1 day.

EudraCT number: 2016-001888-36

For objective response and clinical benefit, patients without any post-baseline assessment will be considered non-responders.

For patients with AR-V7 status not available at baseline, we will assume the AR-V7 status provided at end of treatment or progression, whichever occurs first. Patients with AR-V7 status not available in the study will be considered as AR-V7 negative.

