5.2. Treatment phase: Assessments

All screening assessments must be completed and reviewed to confirm that patients meet all eligibility criteria before treatment starts (day 1). The investigator will maintain a screening log to record details of all patients screened and to confirm eligibility or record reasons for screening failure, as applicable.

Visits are organized in programmed cycles of 28 days (if there are no delays in treatment owing to the occurrence of a side effect). Adjustment of dose level is not permitted. Dose delays are permitted, as described in section 6.11. All visits must occur within \pm 7 working days from the scheduled date, unless otherwise noted in the schedule of assessments. All assessments will be performed on the day of the specific visit unless a time window is specified. Assessments scheduled on the day of study treatment administration should be performed prior to study treatment administration unless otherwise indicated. If a mandatory procedure described in the protocol falls on a bank holiday and/or weekend, this procedure should be performed on the day before or after the holiday (i.e. within a period of \pm 3 working days).

Local laboratory tests scheduled for day 1(before treatment) of all cycles must be performed within 72 hours prior to confirm to the patient if treatment can be followed up. The results of local blood tests should be reviewed, and this review recorded before administration of the study treatment.

Specific study assessments during treatment phase:

During basic safety visits: Day 1of each cycle (every four weeks):

- Assessment of symptoms.
- Physical examination and measurement of weight, vital signs, and ECOG performance status.
- Basic blood test that includes blood count, coagulation, chemistry with renal function analysis (serum creatinine, creatinine clearance according to the Cockcroft-Gault formula), liver function (AST, ALT, AF, GGT, total and direct bilirubin), glucose, sodium, potassium, calcium, chloride, magnesium, uric acid, total protein, albumin, and lactate dehydrogenase.
- PSA determination.
- HRQoL questionnaire (FACT-P, Version 04).
- Assessment of concomitant medications.
- Assessment of AEs.
- Survival.

During full visits: Day 1 of each cycle every three cycles (every 12 weeks):

- Assessment of symptoms.
- Physical examination and measurement of weight, vital signs, and ECOG performance status.

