**Appendix I**

Table 1. Censoring rules for PFS

Situation	Date of progression or censoring	Outcome
Progression documented between scheduled visits	
Earliest of:
 

• Date of radiological assessment showing new lesion (if progression is based on new lesion); or

• Date of last radiological assessment of measured lesions (if progression is based on increase in sum of measured lesions); or

• Bone lesion progression (appearance of <math>\geq</math> two new bone lesions compared to baseline); or

• Presence of symptomatic skeletal events (pathological fractures, spinal cord compression, radiation or surgery to bone)

	Progressed
Death before first progression disease assessment	Date of death	Progressed
Death between adequate assessment visits	Date of death	Progressed
No progression	Date of last radiological assessment of measured lesions	Censored
Treatment discontinuation for undocumented progression	Date of last radiological assessment of measured lesions	Censored
Treatment discontinuation for toxicity or other reason	Date of last radiological assessment of measured lesions	Censored
Death or progression after more than one missed visit	Date of last radiological assessment of measured lesions	Censored

EudraCT number: 2016-001888-36

Table 2. Censoring rules for OS

Situation	End date	Status
Death during study follow-up	Date of death	Death
The patient is alive at last follow-up	Date of last follow-up	Censored

EudraCT number: 2016-001888-36

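### SAP 8.5 censors PFS for patients who die without documented progression, contradicting the SAP and protocol passages that count death as an event

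*SAP*

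**What the plan says.** SAP 8.5 (Handling of missing data) opens with a rule for time-to-event endpoints: "patients without a date of disease progression will be analyzed as censored observations on the date of last tumor assessment". It continues: "If no post-baseline tumor assessment is available, patients will be censored at the date of first treatment + 1 day". Death is not mentioned in either sentence. OS has its own paragraph afterwards, so the first paragraph is the one that applies to PFS.

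SAP Appendix I Table 1, which matches protocol Table 2, has a row "Death before first progression disease assessment" and a row "Death between adequate assessment visits". Both carry the date of death and the outcome Progressed. SAP 7.1.1 includes death in the composite PFS definition. SAP 7.5 derives the time from first dose to progression or death, whichever is earlier.

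Both places also have a rule for gaps in assessment. Table 1 censors "Death or progression after more than one missed visit". SAP 8.5 says "Data for patients with an event (progression) who missed two or more scheduled assessments immediately prior to the event will be censored", dated at the last tumour assessment before the gap.

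**The concern.** A patient who receives one dose and dies at week 8, before any on-study scan and without missing more than one visit, is an event at week 8 under Table 1. Under 8.5 as written he is censored one day after first treatment, and about eight weeks of follow-up go with him. A patient who dies after one clean scan is an event at death under Table 1 and is censored at that scan under 8.5.

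The direction is always the same: 8.5 discards failures. The primary test compares a single open-label arm with a fixed median of 3 months, so no control arm suffers the same loss. Protocol 8.6 defends censoring of withdrawals only if dropping out is unrelated to prognosis, and censoring at death plainly fails that condition. SAP 7.6 records that one unplanned interim analysis has already been run. With two codings in the plan, the choice between them could be made after data have been seen.

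**Working it through.** **Which text says what**

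| Situation | SAP 8.5, literal | Appendix I Table 1 and protocol Table 2 |
|---|---|---|
| Death, no progression date, no post-baseline scan | Censored at first treatment + 1 day | Event at death |
| Death, no progression date, at least one scan, no long gap | Censored at last scan | Event at death |
| Documented progression or symptomatic skeletal event, no long gap | Event | Event |
| Progression after two or more missed assessments | Censored | Censored |
| Death after two or more missed assessments | Censored (first sentence of 8.5) | Censored |

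The contradiction lies in the first two rows.

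**Inputs.** From protocol 8.2: null median 3 months, target 6.3, 23 months of accrual plus 11 of follow-up, 52 patients, one-sided 0.05. From SAP 7.1.1: a maximum-likelihood test for an exponential distribution. From protocol Appendix 1: scans every 12 weeks. Assumed, because the documents are silent: exponential PFS, and the share of failures that are deaths without documented progression.

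**Reproducing the plan's sample size.** Events needed: d = [(1.645 + 0.842) / ln(3/6.3)]² = 11.23. With λ = ln 2/6.3, the chance of an event under uniform accrual is 1 − [exp(−11λ) − exp(−34λ)]/(23λ) = 0.892. Then 11.23/0.892 = 12.6, rounded up to 13, and 13/0.25 = 52. The stated figure reproduces, so this test is used below.

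**Effect by hand, true median 3.0.** The estimate is ln 2 × X/D, with X the person-time and D the events. The chance of an event is 0.985, so D = 52 × 0.985 = 51.23 and X = 51.23/0.2310 = 221.7 months. Suppose five patients die unscanned at 1.5 months (illustrative). Under 8.5 five events are lost, and so are 5 × (1.5 − 0.03) = 7.3 months. The estimate becomes 0.693 × 214.4/46.23 = 3.21 instead of 3.00. At a true 6.3 months the same five deaths move it from 6.30 to 6.94.

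**Simulation (20,000 trials of 52).** Reject when ln(λ0/λ̂) × √D > 1.645, where λ0 = ln 2/3 and λ̂ = D/X.

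*Deaths spread over all PFS events, censored at the last 12-week scan, or at day 1 if none:*

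| Share of PFS events | Patients (true 3.0) | Typical estimate, true 3.0 | Rejection, true 3.0 | Typical estimate, true 6.3 |
|---|---|---|---|---|
| 0% | 0 | 2.98 | 0.04 | 6.27 |
| 5% | 2.6 | 3.10 | 0.07 | 6.55 |
| 10% | 5.1 | 3.22 | 0.11 | 6.86 |
| 15% | 7.7 | 3.36 | 0.18 | 7.22 |

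*Only deaths before the first 12-week scan, censored at day 1:*

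| Share of failures before week 12 | Patients (true 3.0) | Mean estimate, true 3.0 | Rejection, true 3.0 | Mean estimate, true 6.3 |
|---|---|---|---|---|
| 5% | 1.2 | 3.06 | about 0.05 | 6.42 |
| 10% | 2.4 | 3.11 | 0.06 to 0.07 | 6.50 |
| 20% | 4.9 | 3.23 | about 0.10 | 6.68 |
| 30% | 7.3 | 3.37 | about 0.15 | 6.85 |

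At a true 6.3 months the rejection rate is about 1.0 under either rule.

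**The case against.** The strongest reply is that 8.5 is only loosely worded. SAP 7.1.1 uses similar shorthand, censoring patients with no progression, and in the same sentence sends the reader to Table 1, where deaths are events. Table 1 also gives a death an entry in its progression-or-censoring date column, so such a patient could be said to have a progression date. A known death date is not missing data. This is good evidence of intention, and it is why the point is not graded higher. It does not remove the conflict. Nothing sets 8.5 aside, and the one-day rule for PFS appears only there, so a programmer cannot work from Table 1 alone.

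The size is also assumed. Entry requires ECOG 0–1, no visceral metastases and a life expectancy of at least 12 months, so unscanned early deaths may be few. With one or two of them, rejection stays close to the nominal 0.05. That stands.

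A reader might infer two stronger claims:

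- *Early failures in general become day-1 censorings.* The documents do not support this. The one-day rule reaches only patients with no post-baseline scan, and documented progressions and symptomatic skeletal events keep their dates. Under the exponential model about 48% of events at a median of 3.0 months, and 29% at 6.3, fall before week 12. Later deaths revert to a real scan.
- *The two missed-visit rules give opposite outcomes.* Treatment visits follow a 28-day cycle ("Visits are organized in programmed cycles of 28 days") and scans a 12-week one. If Table 1 counted dosing visits, a patient who missed weeks 4 and 8 but progressed on the week-12 scan would be censored there and an event under 8.5. But more than one and two or more are the same threshold, with the same outcome. SAP 8.5 uses assessments and visits for the same thing in one sentence ("who missed two or more scheduled assessments immediately prior to the event will be censored at the last tumor assessment prior to the missed visits"), and Table 1 itself speaks of assessment visits. What remains is an unclear unit and a difference in scope: 8.5 names progression only, Table 1 death or progression.

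**Conclusion.** SAP 8.5 is wrong as written for deaths without documented progression, and the plan does not say that Appendix I overrides it. Taken literally it biases the primary median upward. At a true 3.0 months the estimate becomes about 3.1 to 3.4 and one-sided rejection about 0.07 to 0.18 if 5 to 15% of PFS events are such deaths. Rejection is about 0.05 to 0.15 if only 1 to 7 deaths before the first scan are affected. At the 6.3-month target the decision is safe but the reported median is inflated. These sizes rest on exponential PFS and on death shares that the documents do not supply; the contradiction itself rests on the text alone. Because four other places treat death as an event, this is a correction that should be made rather than a fundamental flaw. The missed-visit wording needs clarifying but is not a proven contradiction.

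**What to change.** In SAP 8.5, for PFS:

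- Restrict the first sentence to patients without documented progression, symptomatic skeletal event or death.
- Restrict the one-day rule to patients with none of these and no post-baseline scan.
- State that Appendix I Table 1 governs PFS censoring.

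As a secondary clarification in the SAP, define a missed visit in Table 1 as a missed scheduled 12-week tumour assessment. Make 8.5 and Table 1 agree on whether the gap rule covers deaths. This matters more once 8.5 is corrected: its first sentence will no longer censor a death after a gap, while Table 1 still will. The same edit should say which Table 1 row applies to an unscanned patient who dies after more than one missed visit, since he fits both an event row and a censoring row.

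The cost is a few sentences of SAP text, settled before the final analysis. It needs no new data and leaves the sample size at 52. Protocol Table 2 already counts these deaths as events, so the main correction needs no protocol change. The estimate may be somewhat less favourable than under a literal reading of 8.5.

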### Per protocol set (PP)

All patients that accomplished selection criteria, received the study drug according to protocol timelines and dosing, and had no major protocol deviations. Criteria for determining the PP group assignment would be established by the Steering Committee before the statistical analysis begins. Patients without AR-V7 status in the study will be excluded.

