### **6.1 Protocol Deviations**

Protocol deviations will be recorded in the EXPERIOR database. A by-patient listing of protocol deviations and a by-patient listing of inclusion and exclusion criteria not met will be provided.

Major protocol deviations are defined as those deviations from the protocol likely to have an impact on the perceived efficacy and/or safety of study treatment.

To determine the per protocol set, all protocol deviations will be reviewed prior to database lock to determine which ones should be classified as major deviations. Patients with major protocol deviations will be excluded from the per protocol set.

Major protocol deviations may be discussed in the data review meeting. Criteria for determining full analysis set would be established by the Steering Committee (SC) before the statistical analysis begins.

Major protocol deviations and any action to be taken regarding the exclusion of subjects or affected data from specific analyses are defined below.

A summary of the number and percentage of subjects with a major protocol deviation by type of deviation will be provided. Also, a by-subject listing of major and minor protocol deviations will be provided.

Description	Category	Grade*	Rationale	Comments
Adult < 18 years	Inclusion/Exclusion criteria	Major	Safety	Automatic check
Informed consent form not signed	Inclusion/Exclusion criteria	Major	GCP breach	Automatic check. Patient data could not be used for efficacy assessment
Patient has not histologically confirmed adenocarcinoma of the prostate without neuroendocrine differentiation or small cell features	Inclusion/Exclusion criteria	Major	Efficacy	Manual Review
Patient has not bone metastases due to the prostate cancer and presence of visceral metastases	Inclusion/Exclusion criteria	Major	Efficacy	Manual Review
Serum testosterone of > 1.7 nmol/L (or > 50 ng/dL) at screening	Inclusion/Exclusion criteria	Major	Efficacy Safety	Automatic check
<24 weeks of treatment with abiraterone acetate or enzalutamide within its approved label indication and discontinuation <4 weeks prior to start of study drug at day 1	Inclusion/Exclusion criteria	Major	Efficacy Safety	Manual Review

EudraCT number: 2016-001888-36

Castration-naïve patients treated >six cycles with docetaxel	Inclusion/Exclusion criteria	Major	Efficacy	Manual Review

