No baseline tumor assessment	Inclusion and Exclusion criteria/ Study procedure	Major	Efficacy	If not baseline values any post-baseline data indicating presence of new bone lesions/visceral lesions could be evaluated as evidence of PD Flag if baseline data (CT and bone scans) are >28 days before day 1 cycle 1.

No post-baseline data indicating presence of ≥ 2 new bone lesions or progression as per RECIST 1.1	Study procedure	Major	Efficacy	No evidence of Radiological PD for patients not discontinued due to increased PSA, symptoms or clinical deterioration.
Visits out of window	Study procedure	Minor	Safety	If not performed every 28 days +7 days until EOT; if not performed every 3 months after EOT or if EOS not performed within 3 months after progression, lost to FUP.
Local laboratory tests out of window	Study procedure	Major	Safety	If tests scheduled for day 1 of all cycles (including screening) not performed within 72 hours prior to the dose
Screening assessments out of window	Study procedure	Case by case	Safety	If done >28 days before day 1 cycle 1. Not applicable to local lab tests.
Assessments not done during treatment period (lab value, HRQoL..)	Study procedure	Case by case	Safety	Not applicable to Radiological Assessments. Flag if systematically not done.
Blood sample for translational study not obtained or obtained at incorrect timepoint	Study procedure	Case by case	Efficacy	Depending on which sample is not collected.
Blood sample for translational study obtained out of window at screening	Study procedure	Case by case	Efficacy	Sample not obtained within 72 hours prior to the first dose
Adequate follow-up	Study procedure	Major	Efficacy	If no post-treatment evaluation according to protocol
Prohibited medication was taken	Concomitant medication	Major	Efficacy	If any therapies intended for the treatment of cancer prior to EoT (Cytotoxic chemotherapy, other systemic radioisotopes,

EudraCT number: 2016-001888-36

				radiotherapy, abiraterone acetate, enzalutamide or any antiandrogen)
Prohibited medication was taken	Concomitant medication	On a case by case	Efficacy Safety	If another investigational drug prior to EoT
Subject not withdrawn as per protocol	Administrative and Other	Major	GCP	If data is obtained after withdrawal

\* Major protocol deviation excludes from the full analysis set

\*\* Identification of clinically relevant conditions from the Medical History

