#### **7.2.2 Subgroup Analysis**

The AR-V7-negative and positive cohorts at baseline will be compared for all analysis. All subgroup analysis will be based on the full analysis and per protocol sets. If there are very few AR-V7 patients recruited, outcomes will be only described.

For time to event endpoints (PFS, OS, time to first symptomatic SSE, TTP-AF, and TTP-PSA), we will use the Kaplan-Meier method and Log-Rank test. For binary outcomes we will use Chi-squared or Fisher's exact tests.

We also analyze PFS and OS with multivariable Cox proportional hazards models including AR-V7 status, CTCs levels and other relevant baseline covariates, including PSA level, number of prior hormonal treatments, the presence or absence of visceral metastases, the Eastern Cooperative Oncology Group (ECOG) score, and prior use of abiraterone acetate or enzalutamide. All tests were two-sided, and P values of 0.05 or less were considered to indicate statistical significance. We will examine the residuals to assess model assumptions and only first-order interactions will be evaluated. We will calculate relative risk (RR) and HR with corresponding 95% CI to compare dichotomous and time to event variables, respectively.

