### 8.2 *General Methodology*

Definition of baseline: For each safety or efficacy parameter, the last valid assessment made before first study drug administration will be used as the baseline for all analyses of that safety or efficacy parameter unless otherwise specified.

Continuous data will be summarized in terms of the number of observations, mean, standard deviation (STD), median, minimum, maximum, first and third quartiles and NA (not available), unless otherwise stated. Where data are collected over time, both the observed data and change from baseline will be summarized at each time point.

The minimum and maximum will be reported to the same number of decimal places as the raw data recorded in the database. The mean, median and first and third quartiles will be reported to one more decimal place than the raw data recorded in the database. The STD will be reported to two more decimal places than the raw data recorded in the database. In general, the maximum number of decimal places reported shall be four for any summary statistic.

Categorical data will be summarized in terms of the number of subjects providing data at the relevant time point (n), frequency counts and percentages. Changes from baseline in categorical data will be summarized using shift tables where appropriate.

Percentages will be presented to one decimal place. A percentage of 100% will be reported as 100%. Percentages will not be presented for zero counts. Unless otherwise EudraCT number: 2016-001888-36

stated, percentages will be calculated using n as the denominator; for frequency tables not assessed by time point the number of patients considered for every analysis set will be used as denominator. If sample sizes are small, the data displays will show the percentages, but any textual report (e.g. clinical study report) will describe frequencies only.

P-values greater than or equal to 0.001, in general, will be presented to three decimal places. However, if a p-value is only presented to four decimal places it will not be rounded again but will be presented to four decimal places. P-values less than 0.0001 will be presented as “<0.0001”.

Confidence intervals will be presented to one more decimal place than the raw data. A two-sided significance level of 5% will be used for confidence intervals.

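### SAP 8.5 lets the baseline AR-V7 cohort label be read at the PFS event and counts untested patients as negative; no planned analysis is sure to use measured pre-dose status only

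*SAP*

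**What the plan says.** SAP 8.5 (Handling of missing data) has two rules for AR-V7. If the baseline result is missing, "we will assume the AR-V7 status provided at end of treatment or progression, whichever occurs first". If there is no result at any time, "Patients with AR-V7 status not available in the study will be considered as AR-V7 negative".

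These labels feed SAP 7.2.2: "The AR-V7-negative and positive cohorts at baseline will be compared for all analysis". The same section puts AR-V7 status into the Cox models for PFS and OS. It also has a fallback: "If there are very few AR-V7 patients recruited, outcomes will be only described". No threshold is given for that fallback.

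The general definition in SAP 8.2 is that "the last valid assessment made before first study drug administration will be used as the baseline for all analyses". That sentence allows for exceptions specified elsewhere, and 8.5 is one.

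Two other parts of the SAP bear on the same patients:
- The per protocol set has its own AR-V7 rule: "Patients without AR-V7 status in the study will be excluded".
- The deviation table in SAP 6.1 lists "Blood sample for translational study not obtained or obtained at incorrect timepoint" and leaves its grade to individual judgement, depending on which sample is missing.

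**The concern.** The comparison is meant to relate status before treatment to later PFS. The back-fill rule takes the label from a sample whose timing is set by the outcome. Under Protocol Appendix 1, footnote 11, a patient who ends treatment for progressive disease sends a single sample at that point. If his baseline result is missing, his baseline label is then read at the PFS event. The SAP cannot treat later status as equal to baseline, because change in AR-V7 on treatment is one of its molecular endpoints (SAP 5.2).

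The second rule places unmeasured patients in the negative cohort. A patient without a baseline result who dies or is lost before a later sample becomes negative by default, so this label can also depend on follow-up.

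AR-V7 is tested retrospectively (SAP 4.7), so a failed baseline assay may come to light after dosing, when it can no longer be repeated.

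At stake are the secondary objective on AR-V7 and PFS, the AR-V7 subgroup tests and the AR-V7 term in the Cox models. A spurious association, or a diluted real one, could not be told apart from the labelling rule.

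**Working it through.** **1. Does any planned analysis avoid the filled labels?**

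- Full analysis set: both 8.5 rules apply.
- Per protocol set: it drops patients with no result at any time. A patient lacking only the baseline sample stays unless that deviation is graded major, and the grade is not fixed in advance.
- Modified full analysis set: it requires a CTC determination, with no time point and no AR-V7 condition.

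Exclusion of back-filled patients is therefore possible but not guaranteed. It is also unclear which set would lose them. The text of SAP 6.1 says "Patients with major protocol deviations will be excluded from the per protocol set", while the footnote to its table says a major deviation removes the patient from the full analysis set.

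**2. Inputs from the documents** (Protocol 8.2, SAP 4.7, Protocol Appendix 1)

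- 52 patients, 25% positive (13 and 39).
- Target median PFS 6.3 months against 3 months, one-sided 5%, 80% power.
- 23 months of uniform accrual plus 11 months of follow-up.
- Week-24 assessment at the end-of-treatment visit after six cycles.

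The plan's sample size reproduces under an exponential model:
- Events needed: (1.645 + 0.842)² / [ln(3/6.3)]² = 11.2.
- Probability of an event by the cut-off at median 6.3 months: 0.892.
- 11.2 / 0.892 = 12.6, rounded up to 13 positives; 13 / 0.25 = 52.

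**3. Assumed inputs.** The documents give no missing rate and no conversion rate. The simulation takes 10%, 20% or 40% of baseline results missing at random. The later sample is taken at progression or week 24, whichever is first, and is always available in the back-fill cells. With median 6.3 months, 1 − 2^(−5.52/6.3) = 46% progress before week 24 (5.52 months).

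**4. No true effect.** Two-sided 5% log-rank, 160,000 runs per cell, simulation SE 0.06 points. With complete labels the test already rejects in 5.8–5.9%, so that is the reference, not 5.0%. Column heads give the share of negatives who convert if they progress before week 24, against otherwise. Brackets give the hazard ratio (HR, positive versus negative) that would be read.

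| Missing | Back-fill, 30–50% vs 5% | Back-fill, 15% vs 5% or 30% vs 15% | Back-fill, 30% in both | Baseline only |
|---|---|---|---|---|
| 10% | 6.5–7.0% (1.04–1.07) | 6.1% (1.01–1.02) | 5.8% | 5.9–6.0% |
| 20% | 7.2–9.0% (1.07–1.13) | 6.3–6.5% (1.03–1.04) | 5.7% | 6.1% |
| 40% | 9.4–14.8% (1.14–1.27) | 6.8–7.1% (1.06–1.08) | 5.7% | 6.5–6.6% |

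**5. True HR of 2.0.** 80,000 runs per cell, SE 0.18 points. Power with complete labels is 56%.

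| Missing | HR read, back-fill, 30% convert in both | HR read, unknown as negative | Power, baseline only | Power, back-fill, stable status | Power, back-fill, 30% convert in both | Power, unknown as negative |
|---|---|---|---|---|---|---|
| 10% | 1.85 | 1.96 | 52% | 56% | 49% | 52% |
| 20% | 1.74 | 1.92 | 48% | 56% | 44% | 47% |
| 40% | 1.59 | 1.85 | 39% | 56% | 36% | 38% |

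The unknown-as-negative shift is small: at 20% missing, ln(2.0/1.92) = 0.04. The standard error of the log HR is √(1/11.6 + 1/34.8) = 0.34, with 13 × 0.892 = 11.6 and 39 × 0.892 = 34.8 events.

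**6. A different set of assumptions gives the same pattern.** Here 20% of patients with a missing baseline also lack a later sample, and conversion is confined to negatives with below-median PFS (4,000 runs per cell). If 40% of them convert, the null rejection rate is 6.9%, 7.8% and 10.0% at 10%, 20% and 30% missing. Measured pre-dose labels give 6.5%, 6.6% and 6.7%. If 20% convert regardless of PFS, there is no inflation, but a true HR of 2 reads 1.97, 1.90 and 1.80.

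**The case against.** **The per protocol set already covers untested patients.** This is true. All secondary and subgroup analyses are run in that set as well, so a comparison without never-tested patients exists. With the small shift in step 5, this makes the unknown-as-negative rule the lesser half of the point. It does not deal with back-filled patients.

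**The rule is pre-specified.** Also true: SAP 8.2 permits exceptions, so there is no contradiction. Pre-specification does not make a label read at the event a baseline label.

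**The sizes rest on assumptions.** They do. The 14.8% needs 40% missing and 50% against 5% conversion, although the pre-dose sample is a scheduled procedure. At 10–20% missing the steep case mislabels only about 0.6 to 2.0 patients. The back-fill cells assume every later sample exists and the unknown-as-negative cells assume none does, so each is an upper bound and they cannot be added. Timing matters too. If progression is seen only at 12-weekly scans, 26% are detected before week 24 and the steep case falls to 5.7–6.4%, 6.4–7.7% and 7.7–10.5%. Counting progression found at the week-24 scan as early largely removes that reduction.

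**A failed sample might be noticed in time.** Protocol Appendix 3 has blood received and processed within 24 hours, so a lost tube could be spotted early. A failed AR-V7 assay need not be, because that test is retrospective.

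**The conflict in SAP 6.1 over analysis sets is a general defect.** Agreed; it adds no weight here beyond leaving the handling of these patients open.

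**A baseline-only rule costs power.** It does if AR-V7 is stable. This is the strongest argument for keeping back-fill as a secondary view.

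**Conclusion.** The concern holds, at minor severity. A label called baseline can be taken from a sample at the PFS event, and no planned analysis is sure to rest on measured pre-dose status.

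The direction of the bias is not fixed. Conversion concentrated in early progressors creates or inflates an association; conversion unrelated to progression dilutes one. At 10–20% missing the effect is small unless conversion differs steeply between early progressors and the rest. It becomes material only with much missing data or a steep contrast, and the documents allow neither to be confirmed or excluded.

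The total-sample primary decision (SAP 7.1.1) does not use the labels. The AR-V7 comparison has only 56% power at an assumed HR of 2.0 even with complete data, and it reverts to description if very few AR-V7 patients are recruited. The deviation listing and baseline tables would partly show how many patients lack a baseline result, but not which rule filled each label.

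**What to change.** - In SAP 8.5, define the AR-V7 cohorts for the positive-versus-negative comparisons and the Cox term by the last valid pre-dose result, as in SAP 8.2. Patients without one are left out of those comparisons and stay in all whole-sample analyses as unknown.
- Keep back-fill and unknown-as-negative as sensitivity analyses, and report how many patients each rule affects.
- In the per protocol definition and the SAP 6.1 table, state one handling for patients without a baseline AR-V7 result in place of individual grading.
- If the sponsor keeps 8.5 as the main rule, the minimum is one baseline-only sensitivity analysis with these counts.

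The change is SAP wording only. The price is fewer labelled positives: 13 × 0.9, 0.8 and 0.6 = 11.7, 10.4 and 7.8 at 10%, 20% and 40% missing. Back-fill gives 13.0 if status is stable, or 13.6–14.0, 14.3–15.0 and 15.6–17.0 with steep conversion. If status is stable, the loss of power at HR 2.0 is about 4, 8 and 17 points. If 30% convert in both groups, back-fill is the weaker rule, and against unknown-as-negative nothing is lost. Retaining back-fill as a sensitivity analysis keeps the information it carries.
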